18.8.1.2 Missing dates handling

The following rules will apply to ensure the completion of start/end dates for all CS:

- For start date:
 - If the start date of the medication/procedure is unknown (i.e. complete missing date), the start date will be imputed with the date of 1st of January 2015 (one year before the year the trial started).
 - If both day and month are missing, but the year is available, the date will be imputed to the 1st of January.
 - If the day is missing only, it will be imputed to the first day of the month.

If the stop date is complete or partially missing, and the imputed start date is after the stop date then the start date will be imputed using the stop date

- For end date:
 - If the end date of the CS is unknown (i.e. complete missing date and end relative to reference time point is not equal to ONGOING), the end date will be imputed to the 31st of December 2099.
 - If both day and month are missing, but the year is available, it will be imputed to the 31st of December.
 - If the day is missing only, it will be imputed to the last day of the month.

If the imputed stop date is before the start date then the imputed stop date will be equal to the start date.

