18.8.1.3 Conversions

Table 49 and Table 50 provide conversions to be performed in order to assess the CS dosage:

Table 49: Conversion factors in prednisone equivalent

Who-drug Term	Conversion factor in prednisone equivalent
METHYLPREDNISOLONE	1,25
METHYLPREDNISOLONE SODIUM / METHYLPREDNISOLONE SODIUM SUCCINATE	1,25
METHYLPREDNISOLONE ACETATE	1,25
HYDROCORTISONE / HYDROCORTISONE SODIUM SUCCINATE	0,25
BETAMETHASONE	8.333
BETAMETHASONE DIPROPIONATE	8.333
BETAMETHASONE VALERATE	8.333
BETAMETHASONE PHOSPHATE	8.333
DEXAMETHASONE	6,667
TRIAMCINOLONE / TRIAMCINOLONE ACETONIDE	1,25
CORTISONE	0,2
PREDNISOLONE	1
PREDNISONE	1
DEFLAZACORT	0,83333
MEPREDNISONE	1,25
PARAMETHASONE	2,5
CRONOLEVEL	8,333
BETROSPAM	8,333

Table 50: Frequency conversions for CS

Frequency	Conversion factor	Numerical Conversion factor
OAM	1/30	0,0333
QOD	1/2	0,5000
QW	1/7	0,1429
QWK	1/7	0,1429
BID/Q12	2	2,0000
TID/Q8	3	3,0000
QD – including QD with AM or PM (e.g. QD(AM), QD(PM), QD at AM, QD at PM)	1	1,0000
ONCE	1	1,0000
QAM	1	1,0000
Q2H	12	12,0000
Q3H	8	8,0000
Q4H	6	6,0000
Q6H	4	4,0000
Q8H	3	3,0000
Q12H	2	2,0000
QHS	1	1,0000
QID/Q6	4	4,0000
QPM	1	1,0000
QH	24	24,0000
Q3W	1/21	0,0476
TIW or Three times a week	3/7	0,4286
Four times a week	4/7	0,5714
Q4W	1/28	0,0357
BIW or Twice a week	2/7	0,2857
EVERY 3 HOURS	8	8,0000
X1	1	1,0000
EVERY OTHER DAY	1/2	0,5000
EVERY OTHER DAY ALTERNATLY WITH 30 MG QOD	1/2	0,5000
EVERY OTHER DAY ALTERNATLY WITH 20 MG QOD	1/2	0,5000
ONCE A WEEK	1/7	0,1429
QD (EVERY MORNING)	1	1,0000
SINGLE DOSES	1	1,0000
ALTERNATE DAYS	1/2	0,5000

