18.8.1.4 Corticosteroid usage, cumulative and average daily dose

The study protocol defines rules of CS usage during the study. The non-compliance with these rules will be described using data collected in “Concomitant Medications” eCRF form and

subjects' compliance with CS usage rules checked during the medical review and protocol deviation process (i.e. subjects with PD code = PDEV52e).

According to protocol secondary criterion the following criteria will be summarized:

- Cumulative prednisone-equivalent dose (mg) from baseline visit until end of 52-week treatment period. If one subject does not receive any CS between baseline and end of treatment period then his cumulative dose will be set to 0 mg.

Cumulative dose [mg] = sum of (dose per administration * daily dosing frequency * Duration),

with:

- Sum of () = sum of all CS recorded in Concomitant Medication eCRF form, from baseline visit until the end of 52-week treatment period
- Duration = End CS dose date during treatment period – Start CS dose date + 1
- Daily dosing frequency using frequency conversions (See [Table 49](#) and [Table 50](#)).

As CS usage has to be restricted to the period between screening visit and end of treatment period, the following specific rules will be applied only for the calculation of cumulative prednisone-equivalent dose:

- Start CS dose date:
 - If start dose date is before screening date, baseline visit date will be considered as the start date for duration calculation.
 - If start dose date is after end of treatment period, CS will not be considered for duration calculation.
- End CS dose date:
 - If end is missing or after date of last IMP dose + 14 days or CS ongoing, the end CS dose date will be imputed by the last IMP dose date + 14 days for duration calculation. If last IMP dose is missing then end dose date will not be imputed and duration will not be calculated (patient not treated not taken into account in the analysis).
 - If end CS dose date is before baseline date, CS will not be considered
- Average daily steroid dose (mg) from baseline visit until end of treatment period. If one subject does not receive any CS between screening and end of treatment period then his average daily dose will be set to 0 mg.
 - Average daily dose [mg] = $\left(\frac{\text{Cumulative dose [mg]}}{\text{Duration}} \right)$
 - For completers, Duration = Week 52 date – baseline visit date + 1

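### A one-time corticosteroid dose with an incomplete date is stretched over the imputed interval and counted as daily dosing

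*SAP*

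**What the plan says.** All of this is in SAP Appendix 18.8.

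- **Routes (18.8.1.1).** Systemic corticosteroids by any route other than ophthalmic, topical, nasal or inhaled are included, so injections and infusions count.
- **Frequency (18.8.1.3, Table 50).** One-time administrations get the same daily factor as once-daily dosing: "SINGLE DOSES 1 1,0000". ONCE and X1 are treated alike.
- **Incomplete dates (18.8.1.2).** The rules cover every corticosteroid record. For a start date: "If the day is missing only, it will be imputed to the first day of the month". For an end date: "If the day is missing only, it will be imputed to the last day of the month". With only the year known: "If both day and month are missing, but the year is available, it will be imputed to the 31st of December". If the end date is wholly unknown and the record is not marked ongoing, "the end date will be imputed to the 31st of December 2099".
- **Cumulative dose (18.8.1.4).** "Cumulative dose [mg] = sum of (dose per administration * daily dosing frequency * Duration", where "Duration = End CS dose date during treatment period – Start CS dose date + 1". For this calculation only, a start before screening is moved to the baseline visit. An end that is missing or later than last IMP dose + 14 days is cut to that day.
- **Dose by visit (18.8.1.4).** The visit dose is the sum of the corticosteroid doses the subject is on at that visit.

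**The concern.** Widening a partial date is a reasonable convention for maintenance therapy. For one injection it turns a single dose into a daily one, because the factor of 1 is multiplied by the full imputed interval.

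Two groups of results are exposed:

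- **Dose totals.** Cumulative dose is summarised and compared between arms by Wilcoxon test (14.3.5), and average daily dose is computed from it.
- **Dose at visits.** A stretched record adds its full dose to each visit it covers. This feeds the 7.5 mg/day limit in LLDAS (18.1.7), the SRI endpoints with sustained steroid reduction (14.3.1, which refers to Appendix 18.8 for the daily dose) and the clinically meaningful reduction endpoint (14.3.5).

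The visit error can run either way. A false dose after baseline makes a subject fail. A false dose on Day 1 raises the baseline, which can bring the subject into the 14.3.5 group with a baseline dose of at least 7.5 mg and then show a reduction that did not happen.

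**Working it through.** The SAP gives no worked figure for this derivation, so its rule is applied to an example.

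**Inputs from the SAP:** Table 50 factor 1; Table 49 factor 1.25 for methylprednisolone acetate; the imputation rules in 18.8.1.2; the Duration formula and the cap at last IMP + 14 days in 18.8.1.4.

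**Assumptions, not in the SAP:** one 80 mg injection, so 80 × 1.25 = 100 mg prednisone-equivalent; Day 1 on 1 March 2018; screening 28 days earlier; 364 days of IMP, so the cap falls on Day 364 + 14 = Day 378.

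**Formula:** 100 mg × 1 × (end − start + 1).

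| What is recorded | Days counted | Cumulative dose |
|---|---|---|
| 15 June, both dates complete | 1 | 100 mg (correct) |
| Start 15 June, end June with day missing | 16 | 1,600 mg |
| Day missing in both June dates | 30 | 3,000 mg |
| Start 15 June, end year only | 200 | 20,000 mg |
| Start 15 June, end missing | 272 after the cap | 27,200 mg |
| Both dates missing | 378 after the cap | 37,800 mg |

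In general, a dose missing only the day in both dates is counted 28 to 31 times, depending on the month. An injection on Day 100 with no end date gives 378 − 100 + 1 = 279 days and 27,900 mg.

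**Scale.** A year at 7.5 mg/day is 7.5 × 365 = 2,737.5 mg, less than the 3,000 mg from one injection with only the day missing. Over 365 days that injection contributes 3,000 / 365 = 8.22 mg/day to the average daily dose instead of 100 / 365 = 0.27 mg/day.

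**By visit.** The Day 100 record with no end date adds 100 mg at every four-weekly visit from Week 16 (Day 113) to Week 52 (Day 365): (365 − 113) / 28 + 1 = 10 visits. For a false success, take a subject on a steady 5 mg/day whose injection is recorded only by the month containing Day 1. Baseline becomes 105 mg, and a later dose of 5 mg reads as a (105 − 5) / 105 = 95% reduction.

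**Does another rule prevent this?**

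- The exception in 18.8.1.1 concerns records without a usable frequency whose start and stop are already the same day.
- The closing rules of 18.8.1.2 act only when an imputed date would put the start after the stop.
- The cap in 18.8.1.4 limits the overcount but does not remove it.

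**The case against.** The strongest reply is that this is an edge case. Three things must coincide: a one-time frequency, an incomplete date, and an interval overlapping the treatment period. That stands. A reader might infer that the factor of 1 is itself wrong, but it is not: with complete same-day dates, 1 × 1 day counts the dose once.

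A reader might also infer that the year 2099 enters the cumulative dose. It does not, because 18.8.1.4 cuts the end to last IMP + 14 days. The cap is stated for the cumulative dose only, but a visit dose is likewise computed only for visits up to 14 days after the last intake.

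The effect on responder endpoints has limits too. A month-only record normally covers one four-weekly visit, occasionally two. Section 14.3.1 requires the steroid condition on all days from Week 41 to Week 52, so a genuine large dose in that window already fails the subject. Stretching adds a false failure there only by carrying a dose in from outside. Some of these subjects may be non-responders anyway through the EAC, whose charter is not shown.

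Finally, the endpoints are other secondary ones with nominal p-values (14.3), outside the testing hierarchy in 14.1.2.4. The Wilcoxon test limits the pull of a few extreme totals. The planned corticosteroid listing would make such records visible, though it would not correct their duration.

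All this reduces the likely impact. None of it supplies the missing rule.

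**Conclusion.** The gap is real. For ONCE, X1 and SINGLE DOSES with an incomplete start or end date, the rules as written count one administration as daily dosing over the imputed interval: up to 28 to 31 days when only the day is missing in both dates, and up to last IMP + 14 days in the cumulative dose when the end date is missing. In the assumed examples, 100 mg becomes 3,000 mg or 27,900 mg; these totals scale with the assumed dose, the day counts do not.

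This can inflate cumulative and average daily dose, and can place a false dose on visits inside the interval. The SAP does not support the stronger conclusion that means or changes from baseline are driven by such records, since it does not say how many there are. The two primary and the key secondary endpoints do not use this derivation.

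**What to change.** Add to 18.8.1.2 and 18.8.1.4, for the frequencies ONCE, X1 and SINGLE DOSES:

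1. Set Duration to 1 and count the dose once. Do not apply the last-day-of-month, 31 December or 2099 end-date rules.
2. Use whichever of the start or stop date is complete as the administration date.
3. If neither is complete, place the single day by a fixed rule within the part of the known month or year that overlaps the period from baseline to end of treatment.
4. Flag these records in the corticosteroid listing already planned in 14.3.5. State separately how a record with no month or year in either date is handled.

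Simply imputing the start date and setting the end equal to it would not do. A missing start with a known on-study stop would become 1 January 2015. A month-only dose in the baseline month would move to the 1st, before baseline unless Day 1 is the 1st. Section 18.8.1.4 excludes records that end before baseline, so real doses could become 0 mg.

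With the rule above, the example injection contributes 100 mg in each of the tabulated patterns with at least a year known.

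The cost is a short paragraph in the SAP and one programming condition; no new data are needed. Since this version follows review of the primary analysis results, first count the affected records. If there are any, rerun the corticosteroid outputs and identify the change in the CSR. The LTE steroid summaries, which follow 14.3.5, should use the same rule.

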14.3.5 Corticosteroid usage over time

CS usage over time will be analyzed on the mITT set using data collected in “Relevant Previous Medications Details” and “Concomitant Medications” eCRF Forms.

Only CS taken at baseline or after will be taken into account. Any CS with an end date before screening date will not be taken into account in the following analysis.

General rules, missing data handling, conversions and cumulative dose is defined in Appendix 18.8.

The following endpoints will be described for statistical analysis:

- Clinically meaningful reduction in CS dose from Baseline, defined by:
 - A reduction of daily prednisone-equivalent CS dose $\geq 25\%$ to a dose of ≤ 7.5 mg/day by Week 40 + 1 day (i.e. Week 41) and sustained through Week 52

AND

- No new BILAG A organ domain scores and no more than one new BILAG B organ domain score during Weeks 40 + 1 day (i.e. Week 41) through 52.

Subjects withdrawing from treatment before Week 40 or with missing data at Week 40 will be considered as non-responders. The analysis will be performed on the mITT subjects whose CS dose is greater than or equal to 7.5 mg at baseline.

- Change from Baseline to Week 52 in prednisone-equivalent CS daily dose.

Summary statistics for absolute value, CFB and percent CFB by visit during treatment period in prednisone-equivalent CS daily dose will be provided.

- Reduction by visit, from Baseline to Week 52, in prednisone-equivalent CS daily dose of zero to < 25%, 25% to 50%, > 50%, or an increase.

The same table will be produced with the following categories of prednisone-equivalent CS daily dose at Week 52: ≤ 6 mg, > 6 - 7.5 mg, > 7.5 – 10 mg, > 10 – 20 mg, > 20 – 30 mg and > 30 mg. The proportions are based on the observed subjects as the denominator.

- Cumulative prednisone-equivalent CS dose from Baseline until completion of the Treatment Period (absolute value only) will be described using summary statistics.

Cumulative prednisone-equivalent CS dose will be compared between placebo arm and evobrutinib arms with a pairwise non-parametric Wilcoxon rank sum test.

[figure not shown]
All CS doses will be listed for each subject and flagged for any doses not taken into account in calculation of the scheduled-visit dose (e.g. dose taken between two scheduled visits or dose with missing information). Subjects non-compliant with protocol rules on CS usage will be listed based on protocol deviation data (i.e. all subjects with PD code = PDEV52e).

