 - For discontinuers, Duration = Last IMP dose date + 14 – baseline visit date + 1

- If one subject does not receive any CS between baseline and end of treatment period then his daily dose will be set to 0 mg and change from screening value will be equal to 0 mg.
- Prednisone-equivalent daily dose [mg] by visit:
 - The prednisone-equivalent daily dose at visit X is calculated only if visit X is performed during treatment period (date of visit X \leq last treatment intake + 14 days).
 - At a scheduled visit, prednisone-equivalent CS daily dose is equal to the dose the subject is on at the scheduled visit. If several CS are taken at the same scheduled visit then all CS doses should be added. If a prednisone-equivalent CS dose stopped/changed at the scheduled visit date (Week X visit date), then the prednisone-equivalent CS dose started before (Week X visit date - 1 day) will be considered as the CS daily dose for that visit.
 - CS dose taken between two scheduled visits will not be taken into account in calculation of the scheduled-visit dose.
 - For subjects who completed the treatment period, CS dose that started on or after end of treatment will be excluded from the calculation.
 - All comparisons will be done compared to CS dosing at baseline. CS dosing at baseline is defined at CS dose taken the day of baseline visit (day 1). If patient did not receive any CS at baseline then CS dose is set to 0 mg.
 - For defining CS sparing effect endpoint (i.e. sustained reduction by W41 to Week 52), the derivation of prednisone-equivalent CS daily dose will be repeated at Week 40 scheduled visit using a different rule. If a prednisone-equivalent CS dose stopped/changed at the Week 40 scheduled visit date (Week 40 visit date), then the prednisone-equivalent CS dose started after (Week 40 visit date + 1 day) will be considered as the CS daily dose for that visit. Sustained reduction by Week 41 will be then programmed by checking that CS reduction is maintained between this new post-Week 40 (=Week 41) visit and Week 52 visit (i.e. CS dose at Week 52 is less or equal than CS dose at Week 41). The associated conditions related to CS sustained reduction (i.e. CS dose \leq 7.5 mg/day and \leq Day 1 CS dose, CS dose reduction from baseline \geq 25% and CS dose \leq 7.5 mg/day) will be checked for Week 41, 44, 48 and 52 visits.

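### Partial-date imputation makes successive doses of one corticosteroid overlap, and the visit, baseline and cumulative derivations then add them

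*SAP*

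**What the plan says.** SAP 18.8.1.2 completes partial dates record by record. For a start date: "If the day is missing only, it will be imputed to the first day of the month". For an end date: "If the day is missing only, it will be imputed to the last day of the month". If the month is missing too, 1 January and 31 December are used. Its safeguards act within a single record, for example "If the imputed stop date is before the start date then the imputed stop date will be equal to the start date". Nothing compares one record with the next.

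SAP 18.8.1.4 builds every dose from these records.

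- Visit dose: "If several CS are taken at the same scheduled visit then all CS doses should be added".
- Baseline: "CS dosing at baseline is defined at CS dose taken the day of baseline visit (day 1".
- Cumulative dose: the sum over records of dose, daily frequency and duration.
- Dose change at a visit: the rule begins "If a prednisone-equivalent CS dose stopped/changed at the scheduled visit date (Week X visit date), then the prednisone-equivalent CS dose started before" and takes the dose in force the day before. It acts only when the change falls on the visit date itself.

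The sustained-reduction conditions "will be checked for Week 41, 44, 48 and 52 visits". For the clinically meaningful reduction endpoint, SAP 14.3.5 adds an entry condition: "The analysis will be performed on the mITT subjects whose CS dose is greater than or equal to 7.5 mg at baseline".

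**The concern.** Each record carries one dose, one frequency and one duration, so a change of dose closes one record and opens another. If the site knows only the month of the change, the same unknown day sits on both records. The imputation then stretches the old record forward and the new one backward, and the summation rule treats two successive doses as simultaneous. Any single changeover date would give the old dose or the new dose; this derivation gives their sum.

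The steroid dose enters the SRI endpoints with sustained OCS reduction and LLDAS (14.3.1, 18.1.7), and the endpoints of 14.3.5: clinically meaningful reduction, change and categories of dose, and cumulative dose. Day 1 matters most. It is the reference for the comparison with the Day 1 dose, for the 25% reduction and for the 7.5 mg entry condition.

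**Working it through.** The plan gives no figure to reproduce, so the check applies its rules to one dose change. The mg values are illustrations and imply no view on dosing.

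**Step 1, dates.** Old dose a stops, and new dose b starts, on an unknown day of March. By 18.8.1.2 the old record ends on 31 March and the new one starts on 1 March.

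**Step 2, visit dose by day (18.8.1.4).**

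- 2 to 30 March: both records are active and neither starts or stops that day, so the dose is a + b.
- 31 March: the old record stops on the visit date, so the day before is used. Both were active then, so the dose is a + b.
- 1 March: the new record starts on the visit date, so the day before is used. Only the old record was active, so the dose is a.

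The sum is therefore assigned on 30 of 31 days.

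**Step 3, size.** The cumulative dose for the month is derived as 31 × (a + b). The true value lies between 31 × min(a, b) and 31 × max(a, b).

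| Change (mg/day) | Possible true visit dose | Derived visit dose | Derived month total (mg) | Possible month total (mg) |
|---|---|---|---|---|
| 20 to 10 | 20 or 10 | 30 | 930 | 310 to 620 |
| 10 to 5 | 10 or 5 | 15 | 465 | 155 to 310 |
| 7.5 to 5 | 7.5 or 5 | 12.5 | 387.5 | 155 to 232.5 |
| 5 to 2.5 | 5 or 2.5 | 7.5 | 232.5 | 77.5 to 155 |

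In the third row both real doses meet the criterion of at most 7.5 mg/day, but the derived dose fails it. In the fourth row, if the overlap covers Day 1, the derived baseline meets the 7.5 mg entry condition although neither real dose does.

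**Step 4, Day 1 inside the overlap.**

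- Increase from 5 to 10 mg after Day 1, in the Day 1 month. Derived baseline is 5 + 10 = 15 mg; the true baseline is 5 mg. At 7.5 mg through Weeks 41 to 52 the derived reduction is (15 − 7.5)/15 = 50%. The subject passes the 25%, 7.5 mg and Day 1 dose conditions, although 7.5/5 = 1.5, which is 50% above the true baseline.
- Change from 10 to 7.5 mg, then stable. Derived baseline is 17.5 mg and the derived reduction is (17.5 − 7.5)/17.5 = 57.1%. The true reduction is (10 − 7.5)/10 = 25% if the change came after Day 1, and 0% if it came before.

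**Step 5, how often a visit meets the overlap.** Assume exact 28-day visits from Day 1 to Week 52, Day 1 dates spread over two calendar years, and a change day uniform over the study year. More than 99% of change months then contain a visit that takes the summed dose. This is conditional on a dose change with both days missing; how often that happens is not stated.

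**Step 6, variants.** If only one of the two dates lacks its day, the overlap is shorter. If the month is also missing on both, it can run for a calendar year.

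**The case against.** **Reach.** A reader might infer that every day of the month carries the summed visit dose. It does not: a visit on the first takes the previous day's dose. Nor does the error always favour a steroid-sparing result. After baseline the overlap raises the dose and makes response harder to reach; only an overlap on Day 1 can create false responders. Nothing in the SAP suggests that partial dates would differ between blinded arms, so the documents do not support a claim of bias towards evobrutinib. These limits stand.

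**Stakes.** The affected endpoints are other secondary, with nominal p-values (14.3) and outside the testing hierarchy (14.1.2.4). SRI-4 and SRI-6 use no steroid dose (14.1.1), so the primary result is not touched. All corticosteroid doses are listed by subject, and compliance with the steroid rules is checked in medical review. Those checks could expose an overlap but do not correct it.

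**Frequency.** The number of partial dates is unknown, and the Day 1 case needs a change in the Day 1 month. This limits the size that can be claimed. It does not make the rule right.

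**Remedy.** The tempting repair, a flat ban on overlapping records of one drug, would do harm of its own.

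- Table 50 lists alternate-day regimens paired with a second dose, so some overlaps are real and should be summed.
- Ending the old record just before the imputed first of the month can understate a visit dose. With a visit on 10 March and a 10 to 5 mg taper on 20 March, the true dose is 10 mg but 5 mg would be derived.
- Pushing the new record to the day after Day 1 would turn a 10 to 5 mg taper made before Day 1 into a 10 mg baseline. An unchanged 5 mg would then score as a 50% reduction.

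This objection stands and shapes the fix.

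**Timing.** Version 4.0 of the plan follows review of the primary analysis results, so a change to the 52-week steroid derivations is post hoc and must be labelled so. The LTE analysis still derives steroid dose through 14.3.5 against the 52-week baseline (9.6, 14.6).

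**Conclusion.** The point holds. For a dose change with the day, or day and month, missing on both adjoining records, 18.8.1.2 and 18.8.1.4 together assign old plus new at any visit in the imputed period except one on its first day, and they double count the cumulative dose over the period. The errors run both ways: wrongly failed dose criteria after baseline, and an inflated reference dose if Day 1 lies in the period. The conclusion assumes that the records are successive doses of one drug, not concurrent regimens. The effect on trial results cannot be computed because the count of partial dates is not given. With only other secondary, nominally tested endpoints affected, this is a correction that should be made, not a threat to the trial's main conclusions.

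**What to change.** Add to SAP 18.8.1.2 a rule for adjoining records of the same corticosteroid that are successive (not recorded as concurrent or alternating regimens) where at least one of the adjoining dates is imputed: their doses are not summed in the overlap that imputation creates. Then derive:

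- **Day 1 in the overlap:** the lower of the two recorded doses.
- **Post-baseline visit in the overlap:** the higher of the two recorded doses.
- **Cumulative dose:** one changeover at the midpoint of the unknown interval. For 10 to 5 mg in a 31-day month, 15 × 10 + 16 × 5 = 230 mg, inside the possible 155 to 310 mg.

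With the first two rules the unknown day cannot create a steroid-sparing response. In the 5 to 10 mg example the baseline becomes 5 mg, so 7.5 mg at Weeks 41 to 52 is no longer scored as a reduction.

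List the affected subjects, re-run the affected steroid outputs, and identify them in the report as a correction made after the primary analysis.

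The cost is a few lines of text and code, plus the re-run. The derivation becomes slightly conservative for these subjects. For example, a 10 to 5 mg taper really made after Day 1 in the Day 1 month would be given a 5 mg baseline, and that subject would leave the 7.5 mg population.
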